Aim 1. Identify the pathology, structural cell profile (airway fibroblast and epithelial cell) and redox status corresponding to regional areas of fixed and reversible post-bronchodilator defects (BD) in obese asthmatics.

We hypothesize that post-BD fixed defects identified on ¹²⁹XeMRI correspond to sites of increased oxidant stress and airway remodeling and fibrosis. We will use ¹²⁹XeMR imaging to guide bronchoscopy sampling of airways in both BD fixed and BD reversible ventilation defects. We will relate the contribution of the oxidant milieu, structural cell phenotypes and histopathologic composition of airways to changes in ventilation defects observed on ¹²⁹XeMRI.

Aim 2. Define the cellular requirement for redox-mediated TGF-β signaling between airway epithelial cells and fibroblasts driving regional remodeling in obese asthma. We hypothesize that regions of fixed defects on ¹²⁹XeMRI are composed of airway fibroblasts that are more proliferative, invasive and fibrogenic than fibroblasts in BD reversible defects and respond to the increased oxidative milieu and TGF-β signaling. We will assess epithelial cell signaling, airway fibroblast migration/invasiveness, proliferation and extracellular matrix (ECM) protein secretion with *ex vivo* cell culture models. These assays will establish significant associations between airway epithelial signaling and fibroblast function, changes in airway ventilation, and asthma endotypes.

Aim 3 Define regional differences of spatial interactions of mesenchymal cells with epithelial cells in the airway submucosa.

3A - Determine how transcriptional profiles change between lean vs obese asthma and controls;

3B - Determine how transcriptional profiles change in BD fixed vs responsive regions in obese asthma.

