We hypothesize that local gene expression changes and cell signaling among both structural cells and immune cells in airway tissue contributes to airway remodeling in asthma patients with obesity. We plan to utilize spatial transcriptomics techniques to analyze endobronchial tissue samples isolated from asthma and non-asthma participants with and without obesity to compare specific airway tissue gene expression patterns in asthma vs non-asthma participants, participants with obesity vs non-obesity, and combined conditions. These gene expression patterns will be localized to pathologic features of asthma and obesity, including accumulation of submucosal eosinophils, fibrosis, smooth muscle and basement membrane thickening, etc in the tissue sections.

We are collaborating with [name] at Northwestern and Dr's. [name] and [name] (Duke pathologists) for this aim. Cryopreserved airway tissues from deidentified participants will be used for **Aim 3A** and include tables containing the demographics, physiology, FeNO, ACQ and atopy status. Endobronchial biopsies obtained from participants in this study will be deidentified and included in **Aim 3B**.

Purpose of the Study:

The proposed study will determine if sites of abnormal ventilation on $^{129}\text{XeMRI}$ represent areas of airway remodeling and fibrosis enriched with fibroblasts that are invasive, proliferative and fibrogenic. We hypothesize that regional alterations in oxidant stress drive the production of transforming growth factor-beta (TGF- β) which directs pro-remodeling fibroblast functions. We predict that $^{129}\text{XeMRI}$ will be a sensitive and specific biomarker of airway remodeling and fibrosis in obese subjects with asthma.

Primary outcomes:

- We will identify the pathology, structural cell profile (airway fibroblast and epithelial cell) and redox status corresponding to regional areas of fixed and reversible post-bronchodilator defects (BD) in obese asthmatics;
- We will define the cellular requirement for redox-mediated TGF- β signaling between airway epithelial cells and fibroblasts driving regional remodeling in obese asthma;
- We will develop non-invasive 3D imaging techniques to assess airway regional remodeling in obese asthma.

Secondary outcomes:

- We predict that $^{129}\text{XeMRI}$ will be a sensitive biomarker of asthma control and severity of disease.

BACKGROUND & SIGNIFICANCE:

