Following Informed Consent, participants will be enrolled and will be assigned a study ID in consecutive order from the assignment log provided record the assignment on the study log. All enrolled participants will then perform:

- Urine pregnancy for women of child-bearing potential
- Anthropometrics and vital signs
- Medical history review (including the following: age of asthma onset, prior hospitalizations, ER visits, steroid use, frequency of asthma exacerbations, antibiotic use, nocturnal awakenings, frequency of SABA use, immune desensitization, current and past medication use, self-described smoking history)
 - Demographics (race, ethnicity, gender, age)
- ACQ
- Skin allergy testing,
- Blood draw for labs:
 - CBC with diff (LAB1748) 4.0 mL
 - fasting blood glucose (LAB81) 4.0 mL
 - total cholesterol (LAB60) 4.5 mL
 - triglycerides (LAB134) 4.5 mL
 - chemistries (LAB15) 4.5 mL
 - serum IGE (LAB74) 3.5 mL
 - CPT 8.0 mL
 - Total blood volume = 33 mL
- IOS
- Pulmonary function testing will be performed including:
 - exhaled nitric oxide (FeNO),
 - May be repeated once if results are high
 - spirometry
 - Lung volumes via body plethysmography
 - Methacholine challenge

Visit 1 – 4 hours (week 0)

- Urine pregnancy for women of child-bearing potential
- Interim medical history and medications will be reviewed, and any AE's evaluated
- Vital signs

- ACQ
- Standard dose chest CT (SDCT)
- Hyperpolarized ^{129}Xe MRI pre and post bronchodilator.
- Participants will receive a follow up phone call approximately 24 hours after the MRI with the coordinator, including a review of interim medical history and medications and any AE's evaluated

Visit 2 – 2 hours (week 1)

- Standard of Care (SOC) Bronchoscopy consent
- Urine pregnancy for women of child-bearing potential
- Vital signs and brief physical exam
- Interim medical history and medications will be reviewed, and any AE's evaluated.
- Bronchoscopy with BAL 90 ml per airway in two airways for a total of 180 ml, and up to 6 brushes per airway (12 total) and endobronchial biopsies per airway segment (up to 12 total).
- Post-procedure observation in the recovery area of 25 minutes to 1 hour.

The participant will not be allowed to proceed with the bronchoscopy visit which includes moderate conscious sedation without an adult that comes with them during the check in process and is available to escort the participant home.

Visit 3 – follow up (1 week after visit 2)

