- Participants will receive a follow up phone call with the coordinator, including a review of interim medical history and medications and any AE's evaluated

Asthma Cohort Inclusion / Exclusion Criteria are as follows:

INCLUSION

1. Adequate completion of informed consent process with written documentation
2. Male and female patients, 18 - 65 years old, inclusive
3. Physician diagnosis of asthma for > 1 year
4. Able to perform reproducible spirometry according to ATS criteria
5. All racial/ethnic backgrounds may participate
6. BMI ≥ 30 kg/m²
7. Regular treatment with ICS or ICS/LABA and/or LAMA combination medication for at least 3 months; on a stable dose for the 4 weeks prior to Visit 0
8. Smoking history <10 pack years and no smoking in the last 3 months
9. Late onset asthma: Age of asthma onset (diagnosis) ≥ 12 years;
 - FeNO < 25 ppb at Visit 0
 - Negative allergen skin test
10. Early onset asthma: Age of asthma onset (diagnosis) <12 years
 - FeNO ≥ 25 ppb at Visit 0
 - Positive allergen skin test
11. Positive Methacholine challenge- Confirmation of asthma: Either (1) 12% or greater bronchodilator response (BDR) in FEV1 to albuterol at Visit 0 OR (2) PC20 methacholine ≤ 16 mg/ml at Visit 0 (historical results from previous studies or documented in clinical records within preceding year are acceptable alternatives) AND/OR Positive PD40 to X5 and R5 on IOS.

EXCLUSION:

1. Respiratory tract infection within the 4 weeks prior to Visit 0
2. Oral or systemic corticosteroid burst (for any indication) within the 4 weeks prior to Visit 0
 - One-time doses, such as intra-articular injections into a shoulder or knee joint, require a 4-week washout prior to Visit 0
3. Asthma-related ER visit within the previous 4 weeks of Visit 0

4. History of ICU admission/intubation due to asthma in the past 1 year
5. Three or more asthma exacerbations requiring treatment with systemic corticosteroids in the past year consistent with severe asthma
6. Asthma exacerbation requiring systemic corticosteroids within the 4 weeks prior to Visit 0
7. Significant concomitant medical illness, including (but not limited to) heart disease, cancer, uncontrolled diabetes, other chronic lung diseases
8. Chronic renal failure (creatinine > 2.0) at Visit 0
9. Positive urine pregnancy test at Visit 0 or at any time during the study
10. Untreated sleep apnea

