11. Participation in an intervention study (including, bronchoscopy) or use of investigative drugs within the past 30 days or plans to enroll in such a trial during the study
12. Unable or unlikely to complete study assessments in the opinion of the Investigator
13. Study intervention poses undue risk to patient in the opinion of the Investigator
14. Negative Methacholine challenge (historical results from previous studies or documented in clinical records within preceding year are acceptable alternatives) and negative PD40 to X5 and R5 on IOS.

Inclusion Exclusion Criteria for Non-asthmatic controls

INCLUSION

1. No history of asthma or other chronic lung diseases
2. Male and female patients, 18 - 65 years old, inclusive
3. Not currently smoking or using other forms of tobacco-related products (including vaping)
4. Smoking history <10 pack years and no smoking in the past 3 months
5. FEV1 > 80% of predicted and FEV1/FVC > lower limit of normal.
6. Ability to sign consent
7. BMI \geq 30 kg/m²
8. Negative allergen skin test
9. Negative Methacholine challenge (historical results from previous studies or documented in clinical records within preceding year are acceptable alternatives) and negative PD40 to X5 and R5 on IOS.

EXCLUSION

1. Respiratory tract infection within the 4 weeks prior to Visit 0
2. Oral or systemic corticosteroid burst (for any indication) within the 4 weeks prior to Visit 0
 - One-time doses, such as intra-articular injections into a shoulder or knee joint, require a 4-week washout prior to Visit 0
3. Significant concomitant medical illness, including (but not limited to) heart disease, cancer, uncontrolled diabetes, other chronic lung diseases
4. Chronic renal failure (creatinine > 2.0) at Visit 0
5. Positive urine pregnancy test at Visit 0 or at any time during the study
6. Untreated sleep apnea
7. Participation in an intervention study (including bronchoscopy) or use of investigative drugs within the past 30 days or plans to enroll in such a trial during the study
8. Unable or unlikely to complete study assessments in the opinion of the Investigator
9. Study intervention poses undue risk to patient in the opinion of the Investigator
10. Positive Methacholine challenge (historical results from previous studies or documented in clinical records within preceding year are acceptable alternatives)
AND/OR positive PD40 to X5 and R5 on IOS.

Additional Inclusion/Exclusion Criteria for MRI

INCLUSION

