DATA ANALYSIS & STATISTICAL CONSIDERATIONS: For the *ex vivo* studies, conditions will be performed in triplicate and experiments will be independently replicated to ensure reproducibility. For the *in vivo* assessments of airway remodeling and fibrosis (bronchodilator reversibility on ¹²⁹XeMRI), we will compare biomarkers of fibrosis (e.g., trichrome or percent elastic fiber staining) between BD types (fixed and reversible airway segments) both within and between obese asthma groups (early onset, late onset and non-asthma control) using a repeated measures two-way ANOVA with appropriate distributional assumption. Main effects of BD type, obese asthma group and their interaction will be evaluated with repeating BD type within subject (random effect) with compound symmetry variance structure. If significant main effect differences are found, pairwise comparisons between BD types and obese asthma groups will be done using Tukey's post-hoc test. Assuming a 50% decrease in fibrosis between BD fixed and reversible types, a sample size of 10 per group provides our study with ≥80% power to detect an effect size of 0.53 within and 0.60 between groups, where effect size (*f*) is the size of the mean differences relative to the standard deviation and assumed correlation (*p*) within group of 0.30. A p-value <0.05 will be considered statistically significant and all analyses will be performed using SAS version 9.4 or higher (SAS Institute, Inc., Cary, NC). Blinding to conditions and tissue sources will occur across the experimental design. In particular, tissues samples (post-BD fixed and BD reversible tissue based on region) will be blinded to the individual performing the experiments and the individual assays. The key for the tissue samples will be maintained by the program statistician and un-blinding will occur during data analysis by the statistician.

Because of [name] conflict of interest related to ¹²⁹XeMRI, and as required by his Polarean management plan, data analysis and image analysis will be conducted by un-conflicted individuals.

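### A current vaper can be enrolled as an asthma participant but not as a control, so comparisons with the control group may be confounded by an exposure difference that eligibility creates

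*Combined protocol and SAP*

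**What the plan says.** **Asthma cohort.** Inclusion item 8, in both the synopsis and the body (Asthma Cohort Inclusion / Exclusion Criteria), reads "Smoking history <10 pack years and no smoking in the last 3 months". Nothing else in either asthma list concerns tobacco.

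**Controls.** Inclusion items 3 and 4, again in both the synopsis and the body, read "Not currently smoking or using other forms of tobacco-related products (including vaping" and "Smoking history <10 pack years and no smoking in the past 3 months".

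**Data collected.** The Visit 0 medical history names "self-described smoking history". It does not name vaping.

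**Comparisons.** Under Data Analysis & Statistical Considerations, fibrosis biomarkers are compared between segment types "both within and between obese asthma groups (early onset, late onset and non-asthma control". The model is described as "Main effects of BD type, obese asthma group and their interaction will be evaluated with repeating BD type within subject (random effect"; no smoking or vaping term is listed. The same section plans to look for differences in epithelial secreted proteins across early onset, late onset and obese non-asthma participants.

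**The concern.** The controls are there so that a difference from the asthma groups can be attributed to asthma. That needs the groups to be selected alike on other things that act on the sampled tissue. Here one inhaled exposure is barred in the reference group and not named in the asthma groups. The plan gives no reason for the difference.

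Brushings, lavage and biopsies are taken from airways that an inhaled aerosol reaches. If some asthma participants vape and vaping shifts a measured marker, part of an asthma-control difference would come from the eligibility lists and not from the disease. The planned model has no term that would separate the two.

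**Working it through.** **1. The two lists side by side**

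| Rule | Asthma (synopsis and body) | Controls (synopsis and body) |
|---|---|---|
| Under 10 pack years, none smoked for 3 months | Yes, item 8 | Yes, item 4 |
| Not currently smoking | Implied by item 8 | Yes, item 3 |
| No other tobacco products, vaping named | Absent | Yes, item 3 |

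The asthma exclusions and the additional MRI criteria, which apply to everyone, contain no tobacco item. Nothing elsewhere closes the gap.

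**2. Which contrasts are open to it**

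- *Fixed versus reversible segments within a participant.* Both segments come from the same person, so an exposure that acts equally on the whole lung cancels. Only a regionally uneven effect, or an interaction with segment type, would remain.
- *Asthma group versus control.* Nothing cancels. The group main effect in the planned model and the comparison of secreted proteins are both of this kind.
- *Covariate adjustment.* The only adjustment the plan mentions is for demographics, in the spatial transcriptomics analysis.

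**3. Illustrative size**

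The plan states no figure to reproduce here. Both inputs below are assumptions, because the documents give neither.

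Let p be the share of asthma participants who currently vape (0 in controls by rule) and e the shift in a marker, in SD units. The bias in the asthma-minus-control difference is b = p × e.

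| p | Number of 40 | e | b |
|---|---|---|---|
| 5% | 2 | 0.5 SD | 0.05 × 0.5 = 0.025 SD |
| 10% | 4 | 1.0 SD | 0.10 × 1.0 = 0.10 SD |
| 20% | 8 | 1.5 SD | 0.20 × 1.5 = 0.30 SD |

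The sign of b is the sign of e, which the documents do not give. The 40 asthma participants and 10 controls are from Subject Recruitment and Screening.

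For a two-sided 5% t-test of 40 against 10, the noncentrality is b / √(1/40 + 1/10) = b / 0.354, with 48 degrees of freedom. The false-positive rate becomes 5.1% at b = 0.025, 5.9% at b = 0.10 and 13.2% at b = 0.30.

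The chance that at least one of 40 asthma participants vapes, at p = 5%, is 1 − 0.95^40 = 87%.

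**4. Scale against the planned effect**

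The plan's between-group effect size is f = 0.60. Suppose three equal groups, with both asthma groups shifted by d from controls. Then f = d × √2/3 = 0.471d, so d = 0.60/0.471 = 1.27 SD. The illustrative bias is 0.025/1.27 = 2% to 0.30/1.27 = 24% of that difference, and 0.10/1.27 = 8% at the middle row.

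**The case against.** The strongest case is that this is a wording slip with little reach.

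- *Smoking may be meant to include vaping.* The control list names vaping separately, which suggests that it does not. But control items 3 and 4 already overlap on smoking, so the two-item structure does not settle the meaning. What stands is that the asthma text is silent, and staff could apply it differently in the two cohorts.
- *The main hypothesis is not an asthma-control contrast.* A reader might infer that the redox part of the first primary outcome is compromised. The documents do not support that. The outcome is "redox status corresponding to regional areas of fixed and reversible post-bronchodilator defects (BD) in obese asthmatics", and Aim 1 hypothesises that "post-BD fixed defects identified on ¹²⁹XeMRI correspond to sites of increased oxidant stress and airway remodeling and fibrosis". Both are regional contrasts within asthma participants. The biomarkers that the ANOVA text names are fibrosis stains, and no asthma-control test of redox status is spelled out. This objection stands and limits the point to comparisons with controls.
- *The exposure is not confined to asthma.* The control item bars current use and sets no look-back, so former vaping can occur in any group. This also stands: the asymmetry concerns current use.
- *The data could still be captured.* The Visit 0 list is introduced as what the history includes, so asking about vaping is not precluded. It would be too strong to say that the analysis could never deal with it. Capture is not assured, however. And with no current vapers among controls, any vaping effect could be estimated only from asthma participants.

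**Conclusion.** The asymmetry is real, appears in both the synopsis and the body, and is not explained. It may confound the comparisons of asthma groups with controls. It leaves the within-participant contrast of fixed with reversible segments largely intact.

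The size is unknown. The range of 0.025 to 0.30 SD rests wholly on assumed shares of 5% to 20% and assumed effects of 0.5 to 1.5 SD. Bias arises only if current vapers are enrolled and vaping shifts the marker; the documents establish neither, nor the direction of an effect.

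Two further inferences should be resisted. A current cigar smoker is plausibly already barred from the asthma groups by the no-smoking rule, so the gap is vaping and unsmoked tobacco. And nothing in the documents shows that vaping would differ between early and late onset asthma: both groups share item 8 and the same age range, and they are defined by age at diagnosis, not current age.

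This is a cheap improvement worth making, not a flaw that undermines the study.

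**What to change.** 1. Add control inclusion item 3 to the asthma inclusion lists in the synopsis and the body, in the same words.
2. In the Visit 0 history, record current and past vaping and other tobacco-product use for all participants.
3. If asthma participants who currently vape are already enrolled, flag them and repeat the asthma-control comparisons without them as a sensitivity analysis.

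The cost is one eligibility line, one history question and one repeat analysis. The downside is that a few otherwise eligible asthma patients will not be enrolled. Item 2 alone would let the exposure be described, but matching eligibility is cleaner than adjusting for something that cannot occur in the reference group.

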--	---

Inclusion/Exclusion Criteria for Non-asthmatic controls
	
INCLUSION
 
 1. No history of asthma or other chronic lung diseases 2. Male and female patients, 18 - 65 years old, inclusive 3. Not currently smoking or using other forms of tobacco-related products (including vaping) 4. Smoking history <10 pack years and no smoking in the past 3 months 5. FEV1 > 80% of predicted and FEV1/FVC > lower limit of normal. 6. Ability to sign consent 7. BMI \geq 30 kg/m² 8. Negative Methacholine challenge (historical results from previous studies or documented in clinical records within preceding year are acceptable alternatives) and negative PD40 to X5 and R5 on IOS 
EXCLUSION
 
 9. Respiratory tract infection within the 4 weeks prior to Visit 0 10. Oral or systemic corticosteroid burst (for any indication) within the 4 weeks prior to Visit 0 11. One-time doses, such as intra-articular injections into a shoulder or knee joint, require a 4-week washout prior to Visit 0 12. Significant concomitant medical illness, including (but not limited to) heart disease, cancer, uncontrolled diabetes, other chronic lung diseases 13. Chronic renal failure (creatinine > 2.0) at Visit 0 14. Positive urine pregnancy test at Visit 0 or at any time during the study 15. Untreated sleep apnea 16. Participation in an intervention study (including bronchoscopy) or use of investigative drugs within the past 30 days or plans to enroll in such a trial during the study 17. Unable or unlikely to complete study assessments in the opinion of the Investigator 18. Study intervention poses undue risk to patient in the opinion of the Investigator 19. Positive Methacholine challenge- Confirmation of asthma: Either (1) 12% or greater bronchodilator response (BDR) in FEV1 to albuterol at Visit 0 OR (2) PC20 methacholine \leq 16 mg/ml at Visit 0 (historical results from previous studies or documented in clinical records within preceding year are acceptable alternatives) 
AND/OR Positive PD40 to X5 and R5 on IOS.

---	--

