- **Exhaled Nitric Oxide**-This procedure involves exhaling gently into a small, handheld device that measures FeNO. Participants will also undergo measurement of exhaled nitric oxide according to standardized techniques. The risks of this test are minimal. Collection of FeNO involves inhalation to total lung capacity while in a seated position followed by slow exhalation against resistance for 10 seconds. Both children and adults can perform this without difficulty. A trained technician will be present to supervise and support the participant in order to minimize discomfort.
- **Impulse oscillometry:** Using this procedure, the patient breathes through a pneumotachograph which generates a sound wave by a loudspeaker that is superimposed over the subject's normal, quiet, tidal breathing. The patient's airflow and sound wave response is transmitted to the apparatus and used to calculate the various components of resistance to breathing. The risks of this procedure are minimal. Both children and adults can perform the procedure without difficulty.
- **Lung volumes via body plethysmograph pre-bronchodilator** - Body plethysmography Lung volumes will be used to assess the following lung volume parameters: Functional Residual Capacity (FRC), Vital Capacity (VC), and then Inspiratory Capacity (IC)
- **Methacholine challenge**-Participants will be asked to come in for a methacholine challenge after consenting. This test is often used to support the diagnosis of asthma. Methacholine is a chemical that may cause the airways of asthmatics to narrow, but does not affect the airways of people without asthma. The test consists of inhaling increasing doses of methacholine through a nebulizer to assess how quickly your airways narrow. Your airways may tighten slightly as the test proceeds. We are performing the test to see how quickly your airways narrow. We will start with very small doses, gradually increasing the dose of methacholine. Spirometry will be performed after each dose to look for changes in lung function. The procedure will be terminated if you demonstrate a significant change in your pulmonary function test (20% decrease in FEV1) or you reach the highest concentration of methacholine. You will receive albuterol (an inhaler medicine that relaxes the airways) after the test is done to reverse any asthma symptoms. The methacholine challenge test will be done by trained personnel and can take up to two hours to complete.

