Before the test, you will be asked to withhold all short-acting bronchodilators for 4 hours, long-acting bronchodilators for 12 hours, and Tiotropium for 24 hours. You will also be asked to avoid caffeine and alcohol for 8 hours.

For challenge testing, methacholine will be administered via AeroEclipse BAN II nebulizer following guidelines recommended by the American Thoracic Society (ATS), with 1 additional dose, will be used: 0.03125 mg/mL, 0.0625 mg/ml, 0.1250 mg/mL, 0.25 mg/mL, 0.5 mg/mL, 1 mg/mL, 2 mg/mL and 4 mg/mL.

Solutions are prepared using **Provocholine 100 mg in 20 ml**, 1 vial will be required.

Vial	Concentration	Prev	Dil	CalcConc	VolStart	VolEnd
A	16	0	6.25	16	6.25	3.25
B	8	3	3	8	6	3
C	4	3	3	4	6	3
D	2	3	3	2	6	3
E	1	3	3	1	6	3
F	0.5	3	3	0.5	6	3
G	0.25	3	3	0.25	6	3
H	0.125	3	3	0.125	6	3
I	0.0625	3	3	0.0625	6	3
J	0.03125	3	3	0.03125	6	6

The vials will be used in reverse order, starting from the lowest concentration.

- Discard vials A and B.
- Vials are prepared in the order A, B, C, D, E, F, G, H, I, and J but administered to the participant in the order J, I, H, G, F, E, D, and C.
- **Allergy testing** - A skin prick test, also called an allergy skin test, checks for immediate allergic reactions to different substances at once. This test is usually done to identify allergies to trees, grasses and weeds.
- **Chest SDCT**
SDCT (**Standard dose computed tomography**) is a standard medical procedure in lung imaging, widely used clinically and in research. Risks to participants are minimal. The study will involve a small amount of radiation exposure to the subjects. There will be one SDCT scan performed during the study. The scan protocol will be adjusted based on the participant weight. The average weight adult radiation dose is 4 mSv per scan, (8mSv) for the study. This compares to the US limit on radiation workers which is 50 mSv.
- **¹²⁹XeMRI**
Hyperpolarized ¹²⁹Xe is treated as a drug by the FDA and is covered by our existing Investigational New Drug Filing (IND# 109,490), which has been active since 2011 and has reported no SAEs that required medical intervention. The proposed studies will use hyperpolarized ¹²⁹Xe prepared in accordance with the Drug Master File that is part of the IND held by Polarean, Inc. We have been granted the rights by Polarean to cross-reference this IND for our own institutional IND filings. We will continue to follow a ¹²⁹Xe administration protocol that is well established in our hands.

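### The PC20 criterion is 16 mg/mL or less, but the described challenge ends at 4 mg/mL, so a PC20 above 4 and up to 16 cannot be observed and its classification is not stated

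*Combined protocol and SAP*

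**What the plan says.** **Threshold.** In the main-text asthma criteria, inclusion 11 accepts a 12% or greater bronchodilator response, or "PC20 methacholine ≤ 16 mg/ml at Visit 0", and/or a positive PD40 on oscillometry. The synopsis repeats this (asthma item 12). The synopsis list for controls uses the same PC20 figure as an exclusion (item 19: "16 mg/ml at Visit 0 (historical results from previous studies"). The main-text control exclusion 10 says only "Positive Methacholine challenge (historical results from previous studies or documented in clinical records within preceding year are acceptable alternatives"), or a positive PD40. It gives no PC20 figure and has no bronchodilator-response limb.

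**Negative result.** Asthma exclusion 14 is a "Negative Methacholine challenge (historical results from previous studies or documented in clinical records within preceding year are acceptable alternatives) and negative PD40". Control inclusion 9 has the same wording. Neither defines negative.

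**Test.** Under Descriptions of Evaluations and Measures, the concentration list ends "0.5 mg/mL, 1 mg/mL, 2 mg/mL and 4 mg/mL". Below the vial table the instruction is "Discard vials A and B" (16 and 8 mg/mL), with the rest "administered to the participant in the order J, I, H, G, F, E, D, and C". The test ends at a 20% fall in FEV1 or at the top concentration. During the test, "Spirometry will be performed after each dose to look for changes in lung function". Oscillometry is described as a separate tidal-breathing measurement.

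**The concern.** A positivity threshold can be applied only if the test reaches it. Here the test ends below the threshold, so one censored result covers people who are positive by the plan's own definition and people who are negative.

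If that result is treated as negative, two things could follow. An asthma candidate with a PC20 between 4 and 16 could fall under exclusion 14, if PD40 is also negative. A volunteer with a PC20 in that range could meet the control criteria. Classification may also depend on the source of the test, because a result from the preceding year is accepted and nothing states what concentrations it must have covered.

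Group (early onset, late onset, control) is a factor in the planned two-way ANOVA, which is powered on 10 per group. Hyperresponsive people among the controls would probably blur the asthma-control contrast.

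**Working it through.** **1. Top concentration given.** From the vial table, vial A = 100 mg / 6.25 mL = 16 mg/mL. Each later vial mixes 3 mL of the previous one with 3 mL of diluent, which halves it: B 8, C 4, D 2, E 1, F 0.5, G 0.25, H 0.125, I 0.0625, J 0.03125. All ten values match the table. Giving J up to C means eight concentrations with a maximum of 4 mg/mL. The concentration list, the discard instruction and the order of administration all agree on this, so it is not a single misprint.

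**2. Gap to the threshold.** 16/4 = 4-fold, and log2(16/4) = 2 doubling steps. From the lowest concentration to the threshold there are log2(16/0.03125) = 9 steps. The unobserved 2 of 9 describe the concentration scale, not a share of people.

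**3. Largest PC20 the test can return.** With log-linear interpolation between the last two concentrations c1 and c2, with falls r1 and r2:

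log10 PC20 = log10 c1 + (log10 c2 − log10 c1) × (20 − r1)/(r2 − r1)

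A PC20 needs r2 of at least 20. The largest value arises when the fall reaches exactly 20% at 4 mg/mL. For c1 = 2, c2 = 4, r1 = 10, r2 = 20 it is 4.0 mg/mL.

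**4. What Visit 0 can show.**

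| True PC20 (mg/mL) | Under the 16 mg/mL criterion | Visit 0 result |
|---|---|---|
| up to 4 | positive | PC20 observed |
| above 4, up to 16 | positive | >4 |
| above 16 | not met | >4 |

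The last two rows cannot be told apart. The documents give no classification rule, no extrapolation rule and no conversion from concentration to delivered dose.

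**5. Other routes.** A bronchodilator response of 12% or more satisfies inclusion 11, but exclusion 14 makes no exception for it. Depending on what negative means, someone with that response, a >4 challenge and a negative PD40 could meet both. For controls, the bronchodilator-response limb is in synopsis item 19 and absent from main-text exclusion 10.

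**6. Size.** With 10 controls, one misclassified person is 1/10 = 10% of the group. The documents give no PC20 distribution, so no rate follows. As an illustration only, suppose a share p of control candidates had a PC20 above 4 and up to 16, all were treated as negative, and no other criterion caught them. The chance of at least one among 10 is 1 − (1 − p)^10: 40% for p = 5%, 65% for 10%, 89% for 20%, 99% for 40%.

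**7. PD40 (secondary).** PD40 is not defined, nor is the direction of change for X5. Only spirometry is described after each dose, no delivered dose is given, and the stopping rule refers to FEV1 alone. PD40 is therefore not derivable from the procedures as described.

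**The case against.** The strongest reply is that the challenge is a confirmatory screen and does not alone separate asthma from control. Asthma candidates also need a physician diagnosis of more than a year and regular controller treatment. Controls also need no asthma history, FEV1 above 80% of predicted, FEV1/FVC above the lower limit of normal and, in the main text, a negative skin test. The synopsis also describes controls as not responsive to bronchodilator. The fixed-versus-reversible contrast is within subject, so it does not rest on the asthma/control label. All of this stands. It limits the consequence but does not make the threshold applicable.

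A second reply is that the text names a nebulizer and follows a society guideline, so 4 mg/mL on this device might correspond to 16 on another. No output or equivalence is stated, so the documents do not support that reconciliation. If the sponsor relies on one, the criterion should say so.

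Four stronger readings are tempting and not supported:

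- *A PC20 of 4 to 16 is read as negative.* That is a likely consequence of a positive/negative rule, but no text says it. The classification is undefined.
- *A fixed share of positives is missed.* Spreading log2 PC20 evenly up to 16 gives 2/9 = 22%, 2/6 = 33% or 2/4 = 50% from lower bounds of 0.03125, 0.25 or 1 mg/mL. These shares rest wholly on an assumed distribution and ignore the other routes, so they are not misclassification rates.
- *A historical test would show the missing range.* It may; the range such a test covered is not stated.
- *PD40 can never be obtained.* Nothing excludes oscillometry during the challenge, and a PD40 criterion implies it. Its single tick in the Schedule of Events proves nothing, since spirometry is also ticked once and is repeated after each dose.

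**Conclusion.** The contradiction between a threshold of 16 mg/mL and a top concentration of 4 mg/mL is certain. It rests only on the documents' own figures. A Visit 0 PC20 in the two doubling steps above 4 and up to 16 mg/mL cannot be observed, and the plan does not say how the censored result is classified. The eligibility criterion therefore cannot be applied as written to a study test that ends without a 20% fall.

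Misclassification is possible and conditional: it needs the censored result to be treated as negative and the other criteria not to catch the person. No rate is claimed. The firm statement of scale is 10% of the control group per misclassified control. The differing control exclusions in synopsis and main text add to the ambiguity. The PD40 gap is real but secondary.

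**What to change.** Reconcile the PC20 threshold with the concentrations given, across the asthma and control criteria in both synopsis and main text and the methacholine challenge description. This review does not say which is right. After the change:

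- the stated positive/negative criterion should be determinable from the test performed, and be the same in synopsis and main text, for asthma and control groups, and for study and historical tests;
- main-text control exclusion 10 and synopsis item 19 should agree on the PC20 figure and the bronchodilator-response limb;
- a test that ends without a 20% fall should be recorded as PC20 above the top concentration given;
- the PD40 criterion should be reconciled with the measurements described.

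The cost is a protocol amendment to the eligibility and challenge text, and a recheck of participants already classified.
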